5.2 Laboratory Device Monitoring

The reference testing laboratories will maintain a log of all unanticipated device-related complications leading to no test, such as absence of transport media, quantity not sufficient, specimen transport collection system damage or incorrect transport system.

6.0 Statistics

6.1 Study Design

This is a cross-sectional, single visit study to evaluate the diagnostic accuracy of NAATs for the detection of NG and CT from pharyngeal and rectal swab specimens. Study participants will have swabs collected from both the rectum and pharynx, following any specimens taken for clinically indicated testing. Each of the swabs from each anatomic location will be tested for both NG and CT using three different NAATs, with a 4th test collected and tested as a tiebreaker, if needed. [redacted] Diagnostic accuracy will be calculated with respect to an anatomic site infected status (ASIS) reference standard described in Section 3.5. As the reference standard is imperfect, we will report positive percent agreement and negative percent agreement in place of sensitivity and specificity.

One potential limitation of this study is that all three of the tests in the reference standard are NAATs. However, all three tests [redacted]. So while, theoretically, there may be correlation in the errors produced by the three tests, the varied molecular targets and the different methods of capture, amplification and detection should mitigate this concern.

6.2 Endpoints

- Infection status for *Neisseria gonorrhoeae* in the rectum as determined by each NAAT
- Infection status for *Neisseria gonorrhoeae* in the pharynx as determined by each NAAT
- Infection status for *Chlamydia trachomatis* in the rectum as determined by each NAAT
- Infection status for *Chlamydia trachomatis* in the pharynx as determined by each NAAT
- Anatomic Site Infection status as determined by the reference standard (as described in Section 2.3)

6.3 Sample Size

For each assay, PPA and NPA³⁵ will be estimated for each of three diagnostic tests defined by pathogen - anatomical site combinations:

- *Neisseria gonorrhoeae* in the rectum
- *Neisseria gonorrhoeae* in the pharynx
- *Chlamydia trachomatis* in the rectum
- *Chlamydia trachomatis* in the pharynx

Each pathogen/anatomic site combination will be evaluated by constructing 95% Score confidence interval estimates for PPA and NPA and evaluating whether 90% can be ruled out by the lower bound of the CI with reasonable confidence.

NPA is expected to be greater than PPA and there will be considerably more not-infected than infected anatomic site, implying that there will be greater power for evaluating NPA. Thus it will suffice to size the study to evaluate PPA.

Assuming that the true PPA is 96%,¹³ then 157, 174, and 196 evaluable participants that are infected are needed to have 80%, 85%, and 90% power respectively to demonstrate a PPA of greater than 90%. Since all of the participants will contribute to the evaluation of all three pathogen-anatomical site diagnostic tests, it will suffice to size the study for the diagnostic test with the lowest expected prevalence (except CT in the pharynx). The study will be more than sufficiently sized for more prevalent disease.

It is expected that the disease prevalence of NG in the rectum, NG in the pharynx, and CT in the rectum will each be greater than 7.5% in the population under evaluation.^{13,14,16-20} Table 3 summarizes the required number of participants to have 80% and 90% probabilities of obtaining the 157, 174, and 196 evaluable participants that are disease-positive to have 80%, 85%, and 90% power when the true prevalence of disease is 7.5%, 10%, and 12.5%.

Table 3: Sample size required number to have 80% and 90% probabilities of obtaining the 157, 174, and 196 evaluable participants that are disease-positive when the true prevalence of disease is 7.5%, 10%, and 12.5% in order to have 80%, 85%, and 90% power (two-sided alpha=0.05) to conclude that sensitivity is greater than 90% when the true sensitivity is 96%.

| Prevalence of Disease Positive | Power | Required Disease Positive to Obtain Power | Required Sample Size to have 80% probability of obtaining required Disease positive participants | Required Sample Size to have 90% probability of obtaining required Disease positive participants |
|--------------------------------|-------|---|--|--|
| 7.5% | 80% | 157 | 2250 | 2325 |
| | 85% | 174 | 2475 | 2575 |
| | 90% | 196 | 2775 | 2875 |
| 10% | 80% | 157 | 1700 | 1750 |
| | 85% | 174 | 1860 | 1925 |
| | 90% | 196 | 2100 | 2150 |
| 12.5% | 80% | 157 | 1350 | 1400 |
| | 85% | 174 | 1485 | 1530 |
| | 90% | 196 | 1665 | 1715 |

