- Additional sensitivity analyses, including the use of latent class models, will be explored. Details will be in the statistical analysis plan.

Table 5. Use of the ASIS in calculation of the positive and negative percent agreement for the Company 1 Assay (Company 1) and Company 3 Assay (NG only).

| | | ASIS | | |
|---|-----------------------|-----------------------|----------------|---------------|
| | | Infected | Indeterminate* | Not infected |
| Result of Test under Consideration** | Positive/Detected | A | C | E |
| | Negative/Not detected | B | D | F |
| | No result | Exclude from analysis | | |
| | PPA | $A / (A+B+D)$ | | |
| | NPA | | | $F / (C+E+F)$ |

*The middle, indeterminate column will be included in the analyses as “Infected” or “Not infected” as described in the sensitivity analyses below.

**Per the ASIS definition in Section 2.3

If the test under consideration has “no result” because the test was not run and no attempt was made to test the sample or because of invalid ASIS results it will be excluded from the primary analysis.

Comprehensive sensitivity analyses will be conducted. These include:

- Classify indeterminate tests on the basis of symptom status. Include indeterminate tests as Infected if the participant is symptomatic in that compartment. Include indeterminate tests as not infected in the participant is asymptomatic in that compartment.

- Include all indeterminate tests as infected
 - $PPA = (A+C) / (A+B+C+D)$
 - $NPA = F / (E+F)$
- Include all indeterminate tests as not infected
 - $PPA = A / (A+B)$
 - $NPA = (D+F) / (C+D+E+F)$
- Additional sensitivity analyses that consider indeterminate results as “missing” and utilize imputation strategies, and graphical techniques
- Additional sensitivity analyses, including the use of latent class models, will be explored. Details will be in the statistical analysis plan.

There are pros and cons to the manner in which indeterminates are handled and the resulting calculations of PPA and NPA. The primary definition is the most conservative but is biased downwards. If $PPA > 90\%$ under this scenario, then the conclusion of $PPA > 90\%$ is clear. The second and third sensitivity analyses count indeterminates (treat all as infected or not infected, respectively) but may not be conservative for calculations of PPA and NPA.

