5.3. Interim Analysis

5.3.1. Interim Analysis Considerations

The study cannot be stopped at the interim for reaching regulatory goals in order to preserve error rates / coverage probability and to ensure enough data for subgroup analyses. Since the trial cannot be stopped for attainment of the regulatory goal, no adjustment to confidence levels are necessary.

Although it is anticipated that swab collection and data completeness will be high for both anatomical sites, both the Intention-to-Diagnose (ITD) and modified Intention-to-Diagnose (mITD) infection rates⁷, as described in **Table 5**, will be estimated. It is expected that disease prevalence (infection rate) of NG in the rectum, NG in the pharynx, and CT in the rectum will each be greater than 7.5% in the population under evaluation. Disease prevalence of CT in the pharynx is expected to be rare.

Table 5: Infection rate calculation for each test under consideration

Intent-to-Diagnose (ITD) Infection Rate	Number of infected ASIS results for test under consideration / Total number of ASIS results ¹
Modified Intent-to-Diagnose (mITD) Infection Rate	Number of infected ASIS results for test under consideration / Total number of ASIS results with exclusion of invalid results ²
	I infected, not infected, indeterminate and invalid ASIS results. I infected, not infected, and indeterminate ASIS results.

Operationally, a range of scenarios for the unobserved data will be generated at each interim review to assist with the decision making regarding sample size adjustments. To ensure enough infected participants to estimate PPAs with desired precision, the lowest ITD/mITD infection rate across the three assays and the three organism/site combinations (except CT in the pharynx) will be used as the observed rate for interim analysis. Of note, it is assumed that there will be greater precision to evaluate NPA as it is expected that there will be more not-infected results than infected results for each anatomic site.

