Table 6 and **Table 7** illustrate hypothetical scenarios when the observed infection rate after the first 1000 participants is rarer than anticipated (equal to 5%, **Table 6**) or more prevalent than anticipated (equal to 10%, **Table 7**), respectively. For both tables, a range of infection rates for the unobserved data (scenarios A-C) are also presented to demonstrate the probability and corresponding total sample sizes to obtain 150, 175 or 200 disease positive participants, respectively, at the end of study.

If infection is rarer than anticipated, then increases to sample size may be considered as demonstrated in scenario A from Table 6. In this case, should the observed prevalence of 5% remain unchanged for the unobserved data, then enrollment of approximately 3200 total participants would be needed to ensure at least 80% probability of obtaining 150 disease positive participants. However, should the infection rate increase to 9% (Scenario C, **Table** 6), then sample size adjustments may not be warranted.

Alternatively, if infection is more prevalent than expected, a smaller sample size may be considered as demonstrated in scenarios A and B from **Table 7**.

⁷ Fundamental Concepts for New Clinical Trialists. A Evans, S. and A Ting, N. 9781420090871. https://books.google.com/books?id=G1IUPQAACAAJ. 2015. Taylor & Francis.

Sample size adjustments may also be considered if there is evidence that the number of ASIS results categorized as invalid will impact study accrual time and/or data analyses.

Table 6: Hypothetical illustration of simulated infection rates after first 1000 participants and observed prevalence
of 5%

Observed R	Brova	lence of						
TD infectio ate at	n	Disease Positive (%) 5%		sitive (N)				
nterim				pants				
Example Sc	cenarios for Un	observed Dat	a					
	Assumed		Es	Estimated probability (P) and sample size (N) to obtain:				
Scenario	prevalence rate ¹	prevalence rate ²	150 Disease+ total participants		175 Disease+ total participants		200 Disease+ total participants	
			Р	Ν	Р	N	Р	Ν
			<50%	2500	<50%	2500	<50%	2500
Α	5%	5%	80%	3220	80%	3740	80%	4260
			90%	3340	90%	3860	90%	4380
_			64%	2500	<50%	2500	<50%	2500
В	7%	6.2%-6.4%	80%	2589	80%	2956	80%	3323
			90%	2669	90%	3046	90%	3413
			800/	2232	76%	2500	<500/	2500
С	0%	7 20/ 7 60/	80%	-		2500	<50%	2500
L L	9%	7.2%-7.6%	90%	2302	80%	2519	80%	2807
bserved an	ed prevalence r ad assumed prev	alence rates f	or the entire du	ration of study	for a given sa	ample size.	-	the

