5.4.2. Final Analysis Considerations

Note: All dataset derivation programs for this endpoint will undergo independent results verification in accordance with CBAR PROG.10033; validation requirements for analysis programs are stated below.

As noted previously, for all final analyses, data collected from eCRFs or data entered by the laboratories in the laboratory information management system (LIMS) will be used. Data from additional sources such as machine data or issue tracking logs may be reviewed for clarification, but will not be used for analysis.

The result for each diagnostic test will be compared with the ASIS for that anatomic site and organism. PPA and NPA will also be estimated for each diagnostic test with 95% confidence intervals. Confidence intervals will be estimated using the Score method.⁸ If the test under consideration has "no result" because the test was not run and no attempt was made to test the sample, the test result will be excluded from primary analysis. If the ASIS result is invalid, this result will be excluded from the primary analysis.

FDA guidance documents will be followed as part of the primary analysis to incorporate indeterminate ASIS or test results for the test under consideration that are equivocal.⁹ It is recognized that there are pros and cons to the manner in which indeterminates are handled and how these impact the resulting estimates of PPA and NPA. The primary analysis approach is the most conservative and is biased downwards. If PPA is >90% under this scenario, then the conclusion of PPA >90% is clear.

Sensitivity analyses will be conducted as appropriate to evaluate the impact of diagnostic accuracy for a range of scenarios addressing indeterminate ASIS results. This will include counting indeterminate ASIS results against the results for the test under consideration with all combinations of Infected/Indeterminate/Not Infected with all outcomes from the test under consideration (Positive/Equivocal/Negative/No result or Invalid) evaluated. These analyses may not be conservative for calculations of PPA and NPA.

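### The power stated in Protocol 6.3 and Table 3 is that of a sensitivity analysis; the power of the primary PPA, which counts test-negative indeterminate sites as misses, is not given

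*Protocol*

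**What the plan says.** Protocol 6.3 sets the success criterion as "evaluating whether 90% can be ruled out by the lower bound of the CI with reasonable confidence", using the 95% Score interval. The calculation starts from "Assuming that the true PPA is 96" percent and concludes that "157, 174, and 196 evaluable participants that are infected are needed to have 80%, 85%, and 90% power respectively". The Table 3 title describes the same quantity as "power (two-sided alpha=0.05) to conclude that sensitivity is greater than 90% when the true sensitivity is 96" percent. It converts infected counts into enrolment through prevalence alone.

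Protocol 6.6.1 defines the primary PPA differently. In Table 4 (Company 2, and Company 3 for CT) it is A/(A+B+C+F), where F is the cell with a negative assay result and an indeterminate anatomic site infected status (ASIS). In Table 5 (Company 1, and Company 3 for NG) it is A/(A+B+D), where D is the corresponding cell. SAP Tables 12 and 14 agree. A/(A+B+C) and A/(A+B) appear in both documents as the sensitivity analysis that treats all indeterminates as not infected.

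Both documents acknowledge the direction of the primary definition: "The primary definition is the most conservative but is biased downwards" (Protocol 6.6.1) and "The primary analysis approach is the most conservative and is biased downwards" (SAP 5.4.2). For interim re-sizing, SAP 5.3.1 uses "the lowest ITD/mITD infection rate across the three assays and the three organism/site combinations", leaving out CT in the pharynx. It also allows adjustment if "the number of ASIS results categorized as invalid will impact study accrual time and/or data analyses".

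**The concern.** The sample size is justified for a ratio that is not the primary one. Below, F stands for the test-negative, ASIS-indeterminate count in either table. Each F site adds one to the primary denominator and nothing to the numerator, so it acts as a certain miss. The power calculation has no term for it.

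The lower Score bound must clear 90%, so only a few misses are allowed and a handful of F sites among nearly 3,000 participants can use up much of that allowance. An assay that detects 96% of infected sites could then fail more often than Table 3 implies. The effect runs one way: F can turn a success into a failure but cannot create a false claim that PPA exceeds 90%. Both documents disclose the downward bias in the estimate, but neither carries it into the power statement.

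**Working it through.** **Inputs.** Null value 0.90, planning value 0.96, two-sided alpha 0.05 and the Score-bound criterion come from Protocol 6.3. Prevalences and enrolment numbers come from Table 3. The primary PPA comes from Protocol Tables 4 and 5. F is not given anywhere and is varied as an assumption.

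**1. Reproducing the plan's figures.** For infected sites only,

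n = [(1.96·√(0.90·0.10) + z·√(0.96·0.04)) / 0.06]²

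with z = 0.842, 1.036 and 1.282 for 80%, 85% and 90% power. This gives 157.5, 173.8 and 195.6, matching 157, 174 and 196. No term for indeterminate sites enters, so the denominator is A+B+C (A+B in Table 5).

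**2. Applying the same criterion to the primary PPA.** Let n be the number infected and A ~ Binomial(n, 0.96). The lower Score bound exceeds 90% when

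(A/(n+F) − 0.90) / √(0.09/(n+F)) > 1.96.

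At n=196 and F=0 this needs A ≥ 185, so 11 misses among infected sites are allowed. At F=3 it needs A ≥ 188, so 8 are allowed.

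**3. Exact power at exactly the required number infected.**

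| F | n=157 | n=174 | n=196 |
|---|---|---|---|
| 0 | 82% | 84% | 90% |
| 1 | 71% | 74% | 84% |
| 2 | 56% | 61% | 74% |
| 3 | 40% | 45% | 62% |
| 5 | 12% | 30% | 33% |
| 10 | 0% | 0.1% | 1% |

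**4. Power at the enrolment numbers.** The rows of Table 3 for 90% power and 90% probability expect more than 196 infected: 2,875 × 7.5% = 216, 2,150 × 10% = 215, 1,715 × 12.5% = 214. Averaging step 2 over n ~ Binomial(N, prevalence):

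| N, prevalence | F=0 | F=1 | F=2 | F=3 | F=5 | F=10 |
|---|---|---|---|---|---|---|
| 2,875, 7.5% | 92% | 87% | 80% | 71% | 48% | 4% |
| 3,000, 7.5% | 93% | 89% | 83% | 75% | 53% | 6% |
| 3,000, 10% | 98% | 97% | 95% | 92% | 82% | 36% |
| 3,000, 12.5% | >99% | 99% | 99% | 98% | 95% | 70% |

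The 2,150 and 1,715 rows agree with the first line within 0.01. If the 167 participants excluded in SAP section D come out of 3,000, then 3,000 − 167 = 2,833 remain, and power at F=3 is 70% (7.5% prevalence) or 90% (10%).

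**5. How large F might be (illustration only).** Assume independent per-test error rates among uninfected sites, N=2,875 and 7.5% prevalence. Adding up the indeterminate combinations in Protocol Table 2, multiplying by the chance that the assay under consideration is negative, and treating F as Poisson gives:

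| False positive | No result | Equivocal | Mean F | Power |
|---|---|---|---|---|
| 0.5% | 0.5% | 0 | 0.4 | 90% |
| 0.5% | 1% | 0 | 0.8 | 88–89% |
| 1% | 2% | 0.5% | 3.7 | 62–64% |
| 2% | 3% | 0.5% | 10 | 11–12% |

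Where a range is shown, it covers n fixed at 216 and n random.

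**The case against.** The strongest reply is that the calculation contains no arithmetic error and that 6.3 names PPA, the primary measure. If 96% were the planning value for the primary PPA itself, the stated power would belong to it. The wording rules this out: 6.3 speaks of infected participants, Table 3 of disease-positive participants and sensitivity, and enrolment is derived from prevalence. It remains true that 96% is only a planning value. If 97% of infected sites were detected (an assumption), 196 infected with F=2 would still give 93% power.

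A second reply is that safeguards exist. Every indeterminate row of Protocol Table 2 contains at least one equivocal or missing result, and SAP section C lets the independent statistician consider sample-size changes when such results affect the analysis. Indeterminates also enter the denominators of both interim infection rates, so they lower the observed rate slightly. Both points stand, but neither puts a value of F into any power figure.

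Third, F is unknown and may be small. Repeat testing reduces final equivocal and missing results, some assays have no equivocal category, and missing results shared across tests tend to make the ASIS invalid rather than indeterminate. Enrolment was also raised to 3,000. All of this stands and limits the size of the concern. Nor does every F site cost exactly one allowed miss: at n=216, power is 90.5% at both F=0 and F=1.

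Last, the conservatism is deliberate, and the alternative ratios will be reported alongside the primary one. That helps a reader interpret a failed criterion, but it does not make the stated power correct for the primary analysis.

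**Conclusion.** The concern holds. The figures 157, 174 and 196 are right for infected sites alone, but 80/85/90% is the power of the primary analysis only at F=0, and neither document states that assumption.

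The size depends on F and on the number infected. At 7.5% prevalence the loss is material: two or three F sites take the 2,875 row from 92% to 80% or 71%. With 3,000 enrolled and prevalence of 10% or more, three F sites leave power at 92% or higher, or about 90% at 10% prevalence after the 167 exclusions. These results assume 96% detection among infected sites and the Score-bound criterion. This should be fixed because a stated design property is wrong for the primary estimator. It does not invalidate the analysis or threaten a positive conclusion.

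**What to change.** In Protocol 6.3 and Table 3, state that 80/85/90% applies to A/(A+B+C), or A/(A+B) for the Table 5 assays, with indeterminates left out of PPA. Add a small table giving the power of the primary PPA at F = 0, 1, 2, 3, 5 and 10, both at 157/174/196 infected and at the number infected expected in each row of Table 3.

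At any remaining interim review, use the indeterminate count already planned in SAP Table 10 as an upper-bound planning value for F. That table does not split indeterminates by the result of the assay under consideration, so PPA stays unseen.

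The cost is a change of wording and one table, with no new data and no change to the estimator or enrolment. The stated power will look less favourable.

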6.4 Randomization of Swabs

Randomization will be employed to ensure that the swab order distribution is the same for 4 tests, the three NAATs under investigation in the study and the tiebreaker test. SAS software (Cary, NC) will be used to generate permuted blocks with a block size of 24, to ensure that each NAAT and the tiebreaker test would have their swab distributions consisting of 1/4 being first swabs, 1/4 being second swabs, 1/4 being third swabs and 1/4 being fourth swabs.

6.5 Monitoring

The core protocol team will receive monthly reports monitoring study accrual, study conduct and completeness of data and swab collection.

The study will be reviewed by an independent statistician, who will not have an association with the protocol or device companies. The independent statistician will review the progress of the study.

Additionally, the study statisticians will prepare reports for the independent statistician that will include baseline summaries (demographics and symptom status) and will address issues concerning the viability and appropriate execution of the protocol such as accrual, endpoint evaluability, and frequency of tests with equivocal results, invalid results, or no results. Issues with specimen collection will be summarized. The independent statistician will also review and evaluate the rates of disease. Toxicity is not expected given the nature of the study.

The study cannot be stopped at the interim for reaching regulatory goals at this time to preserve error rates / coverage probability and ensure enough data for subgroup analyses. Since the trial cannot be stopped for attainment of the regulatory goal, no adjustment to confidence levels are necessary.

Monitoring design assumptions for appropriate study sizing

Infection rates will be evaluated to determine whether sample size adjustments are warranted. The sample size will not be adjusted based on the observed PPAs and NPAs, which will not be reviewed while the study is ongoing, but may be adjusted based only on the infection rates to ensure enough infected participants to estimate PPAs with desired precision. If infection is more prevalent than expected, a smaller sample size may be accepted. If however infection is rarer than anticipated, then increases to sample size will be considered. The infection rate will be evaluated approximately every 500 participants or every 3 months after the enrollment of the first participant, whichever comes first.

